### **B.6.18. STUDY COMPLETION**

All subjects enrolled in the study are expected to complete all scheduled visits through the

follow up visit 12 Months after Device Activation. However, all subjects who remain implanted at the time of Study Completion will be offered to return for an additional visit 12-months after device activation. A Study Completion CRF should be completed at the end of this visit unless they decide to remain in the study. If the subject decides to decline the additional 12-month visit and there is an ongoing study related adverse event, subjects will be followed until resolution of that adverse event or determination that the adverse event is not expected to change.

Subjects who decide to complete the 12-month visit would also be followed equivalently in cases of ongoing study related adverse events.

### **B.6.19. STUDY SUSPENSION AND TERMINATION**

Subjects will be considered to have completed all study requirements following the completion of the follow up visit 3 Months after Device Activation. All subjects who remain implanted at the time of Study Completion will be offered to return for an additional visit 6-months after device activation.

Each clinical site will be considered to have completed study requirements at the end of the required monitored close out visit. The study will be considered terminated when all of the requirements of this Clinical Study Plan have been fulfilled, all close out visits have been completed and all Sponsor and Investigator reports have been issued and reported to the IRB.

The Sponsor, the Investigators, or the IRB(s) may suspend or terminate the study early at any time. If the study is suspended or terminated prematurely, all subjects that are still enrolled will be terminated from the study. A Study Completion CRF will be completed noting that the study has been terminated. If there is an ongoing study-related adverse event, the subject will be followed until resolution of the adverse event or determination that the adverse event is not likely to change.

Subsequent follow-up of the subjects after study completion will be the responsibility of the subject's personal physician.

The Sponsor reserves the right to terminate the study but intends only to exercise this right for reasons related to the protection of subjects or valid scientific or business reasons. The Sponsor will notify Investigators and IRBs in writing in the event of study termination.

The Sponsor reserves the right to stop the enrollment of subjects at any clinical site at any time after the clinical site initiation. Possible reasons for suspending or terminating a clinical site may include, but are not limited to

- Non-compliance by Investigator
- Failure to obtain proper written informed consent
- Repeated failure to complete or submit CRFs in a timely manner
- Failure to report study-related serious adverse events (SAEs) or unanticipated adverse device events (UADEs) to the Sponsor within 48 hours of knowledge of the event and to reviewing IRB in accordance with its policies

- Repeated failure to comply with clearance of queries generated during monitoring of the study
- Inactivity

## **B.7. STUDY ENDPOINTS**

### **B.7.1. DEFINITION OF ANALYSIS POPULATIONS**

All subjects who receive a permanent SCS system implant and complete the study without any major protocol deviations (that would render their data unevaluable).

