	
reporting, study procedures, and/or confound evaluation of study endpoints, as determined by the Investigator
 
 
6. Has significant cervical stenosis, as determined by the Investigator
 
7. Has facet spondylosis, as determined by the Investigator
 
8. Has mechanical spine instability, as determined by the Investigator
 
9. Has undergone, within 30 days prior to enrollment, an interventional procedure and/or surgery to treat upper limb pain, which is providing significant pain relief
 
10. Has unresolved major issues of secondary gain (e.g., social, financial, legal, such as worker compensation matters)
 
11. Be pregnant as determined by urine testing unless female subject is surgically sterile or post-menopausal. If female, sexually active, and childbearing age, subject must be willing to use a reliable form of birth control.
 
12. Have evidence of an active disruptive psychological or psychiatric disorder as determined by a psychologist
 
13. Have a current diagnosis of a progressive neurological disease as determined by the Investigator
 
14. Have a current diagnosis of a coagulation disorder, bleeding diathesis, progressive peripheral vascular disease or uncontrolled diabetes mellitus
 
15. Have a condition that the Investigator determines would significantly increase perioperative risk
 
16. Any previous history of surgery on the posterior elements (laminectomy, posterior fusion) of the cervical spine
 
17. Have metastatic malignant disease or active local malignant disease
 
18. Have a life expectancy of less than 1 year
 
19. Have an active systemic or local infection
 
20. Have within 6 months of enrollment a significant untreated addiction to dependency producing medications or have been a substance abuser (including alcohol and illicit drugs)
 

Primary Endpoint	The primary efficacy endpoint is the percentage of implanted subjects who respond to DTM SCS therapy at 3-months after device activation. An individual responder is a subject that experiences at least a 50% decrease in upper limb pain relative to baseline assessment.

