### **A.3. STUDY SIZE**

Approximately 45 subjects are expected to complete the 3-month endpoint of the study. Up to 90 subjects may be consented to participate at clinical sites in the United States. A sample size estimate is discussed further in section B.5.5 of this Clinical Study Plan.

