#### **B.5.4.1 SAMPLE SIZE RATIONALE**

There is no statistical hypothesis to be evaluated in this study. It is believed that approximately 45 subjects permanently implanted subjects will be sufficient to evaluate the effectiveness and to collect additional safety data of the DTM SCS programming in the target population at the primary endpoint.

Up to 90 subjects will be consented to participate in the eligibility screening process. Those who do not meet all the inclusion criteria and none of the exclusion criteria will be considered screen failures and will not move into the trialing phase. It is estimated that approximately 55 subjects will be trialed. Only subjects with a successful trial phase will be eligible to move into permanent implantation of the device.

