### **B.6.12. 3 MONTHS AFTER DEVICE ACTIVATION ( $\pm$ 21 DAYS)**

Subjects will visit the study site where they will be assessed for pain, other pain (if applicable), extent of disability, Patient Global Impression of Change, and subject satisfaction. Paresthesia generated by the stimulator will be assessed. Programming adjustments may be made, as needed. Anterior-posterior (AP) and lateral X-ray imaging will be done. Subjects will also be assessed for possible study-related adverse events and medication usage. If there are no ongoing study-related adverse events, the subject will complete the study at this visit. In situations where there is an ongoing study-related adverse event, subjects will be followed until resolution of that adverse event or determination that the subject's condition is stable, at which point the Study Completion CRF should be completed.

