### **B.6.16. DEVICE EXPLANT**

At any time during the study, a subject may elect to withdraw from the study and have the SCS device system explanted. Additionally, an Investigator may elect to explant a device due to an adverse event.

The Investigator must follow the appropriate guidelines set forth by the manufacturer of the device for returning the explanted device and/or lead(s) as well as the accessories (charger, patient remote control).

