### **B.6.17. EARLY SUBJECT WITHDRAWAL**

Although efforts will be made by Investigators and study staff to encourage eligible subjects to remain enrolled in the study, subjects may withdraw early from the study for a number of reasons, including but not limited to:

- Failure of SCS Trial Phase
- Subject request
- Investigator request
- Subject lost to follow-up
- Subject's death
- Adverse events (e.g., intolerable adverse event occurrence that forces subject to stop participation in the study)

If a subject is considering withdrawing from the study due to unsatisfactory effectiveness of DTM SCS programming, the Investigator will attempt to improve therapy during a study visit. When a subject is withdrawn early from the study, a Study Termination CRF will be completed describing the reason for discontinuation. Study staff will contact subjects to remind them about their scheduled visits and make sufficient efforts to locate a subject that is not responding to a contact call. If a subject has withdrawn consent for the study, or is lost to follow-up, the completion of this visit is not required. In situations where study withdrawal is due to a study-related adverse event, subjects will be followed until resolution of the adverse event or determination that the adverse event is not likely to change.

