### **B.7.3. PRIMARY ENDPOINT**

Pain rating on the 10 cm Visual Analog Scale (VAS) is considered the primary outcome measure. VAS is the most widely used outcome measure in assessing pain due to its documented reliability and validity, ease in administration, and minimal training requirements for the administrator.

The primary effectiveness endpoint is the percentage of implanted subjects who respond to DTM SCS therapy at 3-months after device activation.

An Individual Responder is a subject that reports a decrease in upper limb pain VAS score by at least 50% at 3 months after activation of the permanent SCS system (Device Activation) as compared with Baseline measurement.

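### The only analysis population is restricted to completers, but the primary endpoint is a percentage of all implanted subjects, so early leavers drop out and the 3-month responder rate is likely overstated

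*Combined protocol and SAP*

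**What the plan says.** B.7.1 contains one entry: "All subjects who receive a permanent SCS system implant and complete the study without any major protocol deviations (that would render their data unevaluable". No all-implanted set or other population is defined anywhere.

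B.7.3 states: "The primary effectiveness endpoint is the percentage of implanted subjects who respond to DTM SCS therapy at 3-months after device activation". The Synopsis says the same: "The primary efficacy endpoint is the percentage of implanted subjects who respond to DTM SCS therapy at 3-months after device activation". A responder is a subject whose upper limb VAS has fallen by at least 50% from Baseline at 3 months.

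The plan foresees exits after implant. B.6.16 says: "At any time during the study, a subject may elect to withdraw from the study and have the SCS device system explanted". It also lets the Investigator explant because of an adverse event. B.6.17 lists adverse events, subject request and loss to follow-up among the reasons for withdrawal. It also addresses dissatisfaction directly: "If a subject is considering withdrawing from the study due to unsatisfactory effectiveness of DTM SCS programming", in which case the Investigator first tries to improve the therapy.

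B.9.2 is purely descriptive and has no rule for missing data. On numbers, A.3 says "Approximately 45 subjects are expected to complete the 3-month endpoint of the study", while B.5.4.1 says "approximately 45 subjects permanently implanted subjects will be sufficient".

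The point of completion varies. B.6.12 says of the 3-month visit: "If there are no ongoing study-related adverse events, the subject will complete the study at this visit". B.6.19 also places completion at 3 months. B.6.18 expects attendance through 12 months. B.6.14 makes the 12-month visit optional, and Table 1 note c records that some subjects consented only to 3 or 6 months.

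**The concern.** The endpoint and the population imply different denominators. Read as written, B.7.1 removes an implanted subject who leaves early, even one with no protocol deviation, because completing the study is a condition of its own. The remark about unevaluable data limits only the deviation condition.

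Those removed are unlikely to be a random sample of the implanted. Explant, adverse events and dissatisfaction are all foreseen routes out. B.6.15 adds another: under remote collection, subjects who stop charging the device or switch it off are not mailed questionnaires until they comply again.

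The study has one arm, no hypothesis and no success threshold, so this percentage is the primary result and will be read at face value. Two analysts, one following B.7.3 and the other B.7.1, could report different rates from the same data. The B.7.1 rate can leave out subjects who stopped because the therapy did not help them.

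**Working it through.** **Inputs from the documents.** About 45 implanted (Synopsis, B.5.4.1) and about 45 reaching the 3-month endpoint (A.3). No expected responder rate, attrition rate or precision target is given.

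**The plan's own figure.** The 45 is a judgement and no formula reproduces it. Using it at both stages implies attrition of 1 − 45/45 = 0%. For scale, 45 subjects at 3 months would need 45/0.90 = 50 implants with 10% loss, or 45/0.80 = 56.25, so 57, with 20% loss.

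**Who is counted under each section.**

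| Implanted subject | B.7.3 denominator | B.7.1 population |
|---|---|---|
| Attends all visits, no major deviation | in | in |
| Explanted and withdrawn, or lost, before 3 months | in | out |
| Major deviation making data unevaluable | in | out |
| Valid 3-month VAS, declines the 12-month visit | in | in if completion is at 3 months, out if at 12 |

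**Formula.** Let p be the responder rate among all implanted, a the fraction leaving before 3 months, and q the rate the leavers would have had.

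- Completer rate = (p − aq)/(1 − a)
- Change = (p − aq)/(1 − a) − p = a(p − q)/(1 − a)

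The change is positive if q < p, zero if q = p and negative if q > p.

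**Worked example (all counts assumed).** 45 implanted, 30 true responders (66.7%, exact 95% CI 51.0 to 80.0), 5 leavers, of whom k would have responded. The last column counts every leaver as a non-responder.

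| k | Completers only | Change (points) | All implanted, missing = non-response |
|---|---|---|---|
| 0 | 30/40 = 75.0% | +8.3 | 30/45 = 66.7% |
| 1 | 29/40 = 72.5% | +5.8 | 29/45 = 64.4% |
| 2 | 28/40 = 70.0% | +3.3 | 28/45 = 62.2% |
| 3 | 27/40 = 67.5% | +0.8 | 27/45 = 60.0% |
| 4 | 26/40 = 65.0% | −1.7 | 26/45 = 57.8% |
| 5 | 25/40 = 62.5% | −4.2 | 25/45 = 55.6% |

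At k = 0 the exact 95% CI for the completer rate is 58.8 to 87.3.

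**Range (assumed p and a), change in points.**

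| | a = 5% | a = 10% | a = 15% |
|---|---|---|---|
| p = 50%, q = 0 | +2.6 | +5.6 | +8.8 |
| p = 66.7%, q = 0 | +3.5 | +7.4 | +11.8 |
| p = 80%, q = 0 | +4.2 | +8.9 | +14.1 |
| p = 66.7%, q = p/2 | +1.8 | +3.7 | +5.9 |
| any p, q = p | 0 | 0 | 0 |

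**The case against.** The strongest reply is that B.7.3 names the endpoint and B.7.1 names who is analysed, so together they mean the percentage of evaluable implanted subjects. The study is descriptive, so no error rate or decision rule is at risk. Subjects have already shown at least 40% relief in the Trial Phase. Pre-visit calls, remote collection and pursuit of missing data should keep losses low. The termination form records reasons for exit, so an all-implanted rate could be rebuilt later. Read literally, B.7.3 even makes a subject without a 3-month report a non-responder.

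Some of this stands. The size of the bias cannot be derived from the documents, and its direction is an inference. The equal figures of 45 are a side matter. The 12-month reading of completion is probably left over from adding later visits, and its bias could go either way.

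The main point is not answered. A joint reading of the two sections is exactly what produces a completer rate under an all-implanted label. Any rule implied by B.7.3 is undone by B.7.1. That the data would allow a repair does not mean the plan prescribes one. In a descriptive study the denominator is most of what the primary analysis has to specify. The confidence interval does not cover the problem, since it reflects sampling error and not systematic exclusion.

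Two objections to the remedy also deserve weight. Counting every missing value as non-response includes exits unrelated to effect, such as pregnancy or termination of the study by the Sponsor, and so can understate the rate. Further, the current version postdates some subjects' 6-month visits, so the primary set would change after open-label 3-month data exist.

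**Conclusion.** The concern holds. As written, the primary endpoint is defined on implanted subjects but analysed only in those who complete the study, with no explicit rule for a missing 3-month VAS. The rate is overstated whenever the excluded respond less often than all implanted subjects. That is likely given the foreseen reasons for leaving, but not certain.

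If leavers are non-responders, losses of 5 to 15% add 3.5 to 11.8 points at a true rate of 66.7%. If leavers respond half as often as all implanted subjects, they add 1.8 to 5.9 points. If leavers respond as often, the effect is nil, and if more often, the rate is understated. All of these rates are assumptions.

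The conflict over when the study is complete is a defect whatever the direction of bias, because one reading discards valid 3-month scores from a 3-month endpoint. This must be fixed before the primary result is reported.

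**What to change.** - **B.7.1:** make the primary analysis set all subjects who receive a permanent implant, matching B.7.3. Count an implanted subject without a 3-month VAS, for whatever reason, as a non-responder.
- **Sensitivity analyses:** report the observed-case rate, and keep the present B.7.1 set, tied to the 3-month visit, as a labelled per-protocol analysis.
- **Completion:** state that attendance at 6 and 12 months does not affect inclusion in the 3-month endpoint. Reconcile the meaning of study completion across B.6.12, B.6.14, B.6.18 and B.6.19.
- **B.9.2:** report the responder rate as n/N with an exact 95% CI.

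The cost is wording, in a formal amendment with Sponsor, IRB and Investigator approval under E.6. No new visits or data are needed. The amendment should give its date and reason and say that some 3-month data already existed.

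The reported rate may fall. The non-responder rule is conservative if some missing subjects did respond: in the example with k = 2 it gives 62.2% against a true 66.7%, 4.4 points low, while the completer rate of 70.0% is 3.3 points high. Showing both, with reasons for exit, lets the reader see how much the choice matters.

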#### **B.6.5. SCS TRIAL PHASE**

Subjects will undergo a Trial Phase with DTM SCS programming. The Trial Phase will last up to 10 days. Percutaneous leads will be placed in the epidural space at a vertebral level based on the subject's pain condition and pain pattern as described in the Physician Implant Manuals. Stimulation will be delivered from an external neurostimulator (ENS).

Anterior-posterior (AP) and lateral X-ray imaging will be done following lead placement at the beginning of the Trial Phase. The subject should flex forward prior to the final AP and lateral X-ray imaging. Additional Imaging may be required if lead migration is suspected throughout the trial.

Stimulation therapy will be as follows:

- Subjects will be given multiple program groups to try. Each DTM SCS program group will have multiple parameters. The stimulation parameters will be within the specifications described in the Intellis™ manuals. Each DTM SCS program group has at least two programs with different pulse rate in the 50 to 1,000 Hz range and each having a maximum pulse width of 1 ms. The subject will progress through each of the program groups until satisfactory pain relief has been reached. The subject will be able to adjust the intensity of the stimulation as deemed needed to obtain pain relief. If sufficient pain relief is not achieved with the initial program group, the subject will be instructed to trial another DTM SCS program group.

Following the standard of care of SCS, adjustments to a program group may be made based on patient feedback following the trialing of a particular program group or set of stimulation parameters. The primary factor for assessing response to a given program group or stimulation parameters is the subject's self-reported pain relief. Adjustments to therapy will be attempted until at least 40% self-reported pain reduction from baseline is achieved or until conclusion of the trial phase (no more than 10 days). Subjects will be assessed for study-related adverse events and medication usage during the duration of the Trial Phase.

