### **B.6.6. END OF TRIAL ASSESSMENT**

At the end of the Trial Phase, subjects will be assessed for pain intensity under optimal therapy parameters. Anterior-posterior (AP) and lateral X-ray imaging may be done at the end of the Trial Phase. The subject will be assessed for study-related adverse events and medication usage.

Subjects who have a "successful Trial Phase" (defined as a 40% or greater pain reduction from Baseline in the upper limbs pain and the subject would like to move forward to the implant phase) will proceed to permanent implantation of a SCS system to evaluate DTM SCS programming. Permanent implantation of the Intellis™ SCS system will be scheduled. A threshold of 40% for the Trial Phase was predetermined as the minimum pain reduction that warrants consideration of a permanent implant and an opportunity to achieve a 50% pain reduction as defined in the Individual Subject Success criterion (see Section B.7.3).

Subjects who did not achieve 40% or greater pain reduction in upper limb and do not receive permanent implantation will exit the study after being followed up for two weeks after removal of the leads to assess study-related adverse events.

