### **B.7.4. SECONDARY ENDPOINTS**

The following secondary endpoints will be evaluated:

- Change from Baseline in upper limb pain mean VAS score determined at the 3-month visit after device activation. This is calculated as: Change from Baseline in Upper Extremities Pain VAS = 3-Month Visit Pain VAS – Baseline Pain VAS. A negative result reflects a decrease in Pain VAS score, while a positive result reflects an increase in Pain VAS score.
- Change from Baseline in extend of disability as measured by mean Pain Disability Index (PDI), evaluated at 3 months after device activation.
- Frequency of treatment emergent adverse events.

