### **B.8.3. SAFETY**

Safety will be assessed by characterizing study-related adverse events at all study visits with descriptive statistics.

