### **B.8.3.2 REPORTING**

Reported AEs, SAEs and UADEs will be assessed and captured from enrollment through the completion of the study on the Adverse Event Source Worksheet. Study-related is defined as relating to the device, procedure or therapy. The assessment/evaluation can be performed initially by a designee, but the Investigator will make the final determination.

Only adverse events that are evaluated by the Investigator to be study-related will be captured on the CRF.

All study-related adverse events will document seriousness, severity, treatment/intervention provided, relationship to the device/procedure/therapy, and resolution.

AEs and SAEs will be reported as required by the IRB.

As would be the common practice when using commercial medical devices, device - related AEs may be reported by the site (per their institutional policy) to the Customer Service or Technical Support of Medtronic as specified in the manufacturer's labeling/manuals.

Data Monitoring Committee will not be used as this is a post-market open label study and will adhere to all IRB reporting requirements and the device manufacturer's reporting requirements.

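### The plan's only analysis population is implanted completers, and no safety set is defined, so adverse event frequency applied as written omits subjects trialed but never implanted and implanted subjects who leave before completion.

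*Combined protocol and SAP*

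**What the plan says.** B.7.1 opens the endpoints section and gives a single set: "All subjects who receive a permanent SCS system implant and complete the study without any major protocol deviations", the deviations being those that make the data unusable. No safety, trialed or all-implanted set appears elsewhere.

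B.7.4 lists among the secondary endpoints "Frequency of treatment emergent adverse events", with no denominator.

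Adverse events can end participation or lead to removal of the device. B.6.16 states that "an Investigator may elect to explant a device due to an adverse event", and B.6.17 gives as a reason for early withdrawal an "intolerable adverse event occurrence that forces subject to stop participation in the study".

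Events are nevertheless collected well beyond the B.7.1 set:

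- B.6.5: "Subjects will be assessed for study-related adverse events and medication usage during the duration of the Trial Phase".
- B.6.6: subjects who miss the trial threshold and are not implanted "will exit the study after being followed up for two weeks after removal of the leads to assess study-related adverse events".
- B.8.3: "Safety will be assessed by characterizing study-related adverse events at all study visits with descriptive statistics".
- B.8.3.2: "Reported AEs, SAEs and UADEs will be assessed and captured from enrollment through the completion of the study".

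B.5.4.1 plans about 55 subjects trialed and about 45 implanted.

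**The concern.** Collecting safety data is a secondary objective (B.2). The study has one arm and no data monitoring committee, so the reported event frequency is its main safety result.

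A set restricted to implanted completers is selected partly on the outcome it is meant to measure. An event serious enough to prevent implantation, or to make an implanted subject leave early, also removes that subject from the count. Trial subjects are genuinely exposed: leads are placed in the epidural space, section C.1 lists bleeding and paralysis among the risks of that placement, and C2 notes that needle insertion carries more risk at cervical levels. A report could follow the plan to the letter and still omit the events that ended participation.

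**Working it through.** **1. The plan's own figures.** There is no event rate, dropout rate, hypothesis or target precision to reproduce (B.5.4.1, B.9.2). What can be checked is the flow of subjects:

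- Trialed but not implanted: 55 − 45 = 10, and 10/55 = 18.2%.
- Implanted among those trialed: 45/55 = 81.8%.
- A.3 expects about 45 to reach the 3-month endpoint, the same as the number implanted, so the plan allows for no loss after implant.

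**2. Denominator under B.7.1.** With *k* implanted non-completers (assumed), the set holds 45 − *k* subjects and omits (10 + *k*)/55 of those exposed.

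| *k* | B.7.1 set | Omitted |
|---|---|---|
| 0 | 45 | 10/55 = 18.2% |
| 2 | 43 | 12/55 = 21.8% |
| 4 | 41 | 14/55 = 25.5% |
| 6 | 39 | 16/55 = 29.1% |

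**3. Who is omitted under each meaning of completion.** B.6.19 treats study requirements as met after the 3-month visit; B.6.18 expects visits through 12 months. Leaving major deviations aside:

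| Subject | 3-month meaning | 12-month meaning |
|---|---|---|
| Trial leads placed, never implanted | omitted | omitted |
| Implanted, leaves before the 3-month visit because of an event | omitted | omitted |
| Implanted, leaves between months 3 and 12 because of an event | kept | omitted |
| Explanted for an event but attends the remaining visits | kept | kept |

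The last row is possible because B.6.16 does not equate an explant chosen by the investigator with leaving the study.

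**4. Effect on the reported frequency (illustration only).** Let *c* be completers with an event, *w* implanted subjects lost because of an event, and *t* never-implanted subjects with an event. All three are assumed: *c* = 4 (about 10% of completers), *w* from 0 to 6, *t* from 0 to 3, with no other losses.

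- B.7.1 set: *c*/(45 − *w*)
- All implanted: (*c* + *w*)/45
- All trialed: (*c* + *w* + *t*)/55
- Share of subjects with an event who are dropped: (*w* + *t*)/(*c* + *w* + *t*)

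| *w*, *t* | B.7.1 set (exact 95% CI) | All implanted | All trialed (exact 95% CI) | Dropped |
|---|---|---|---|---|
| 0, 0 | 4/45 = 8.9% (2.5 to 21.2) | 4/45 = 8.9% | 4/55 = 7.3% (2.0 to 17.6) | 0% |
| 2, 1 | 4/43 = 9.3% (2.6 to 22.1) | 6/45 = 13.3% | 7/55 = 12.7% (5.3 to 24.5) | 3/7 = 43% |
| 4, 2 | 4/41 = 9.8% (2.7 to 23.1) | 8/45 = 17.8% | 10/55 = 18.2% (9.1 to 30.9) | 6/10 = 60% |
| 6, 3 | 4/39 = 10.3% (2.9 to 24.2) | 10/45 = 22.2% | 13/55 = 23.6% (13.2 to 37.0) | 9/13 = 69% |

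The B.7.1 figure stays between 8.9% and 10.3% while the all-trialed figure runs from 7.3% to 23.6%. That follows partly from holding *c* at 4, but it shows the mechanism: the completer frequency barely responds to events that remove subjects. In the first row the direction reverses, and the completer frequency is the higher one.

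**The case against.** The best defence is that B.7.1 was meant for effectiveness only. It is a sentence fragment under a plural heading, it never says that it governs adverse events, and the effectiveness definitions follow it directly. B.7.3 even expresses the primary endpoint as a percentage of implanted subjects, which is not the B.7.1 set. The safety text points to wider reporting: B.8.3 covers all study visits, Table 1 schedules adverse event monitoring from Baseline through both trial-phase visits, B.8.3.2 starts at enrollment, and B.9.2 promises summaries of all outcome data. Study-related serious events also reach the sponsor within 48 hours whatever the analysis set (E.3).

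Much of this stands. Data capture is not at fault, and wider reporting may well be intended. But none of these sections names a safety denominator or sets B.7.1 aside for the adverse event endpoint. The defence therefore shows a conflict between B.7.1 and the safety sections, and that conflict has to be resolved in the text.

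Three stronger readings are tempting, and the documents do not support them:

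- *Anyone explanted or withdrawn for an event is automatically a non-completer.* On the 3-month meaning a later loss still counts as a completer. B.6.18 and B.6.19 also refer to subjects still implanted at completion, which implies that some may complete without the device.
- *The 10 never-implanted subjects are harmed subjects.* They are the planned difference between 55 trialed and 45 implanted. Under B.6.6 that is mainly a matter of trial response and willingness to proceed.
- *The frequency is bound to be understated, by a known amount.* No event or dropout rates are given, and the direction can reverse.

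**Conclusion.** The point holds as a defect in the defined analysis set. Read literally, the only stated population excludes about 10 of 55 planned trialed subjects (18.2%) before any attrition, and every implanted subject lost before the 3-month visit, including losses caused by an adverse event. Losses after month 3 are excluded only if completion means 12 months.

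Understatement is the likely effect, because an adverse event is itself a route out of the set. The 18.2% rests on the plan's own numbers. Every event frequency in the illustration, and the 0% to 69% range for the share of affected subjects dropped, rests on assumed counts and should not be read as a forecast.

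**What to change.** 1. State in B.7.1 that the existing definition applies to effectiveness analyses only.
2. Add to B.7.1: *Safety population: all subjects in whom trial lead placement is attempted, regardless of implantation, study completion or protocol deviations.*
3. In B.7.4, report adverse event frequency on the safety population for the trial phase (about 55 planned) and on all implanted subjects from implant onward (about 45 planned). Completion should not be a condition of any safety denominator.
4. Reconcile B.6.18 and B.6.19 so that study completion has one meaning, since that meaning decides whom B.7.1 excludes.

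The cost is a few sentences. The study-related events are already collected from enrollment, so no visit or procedure changes. The downside for the sponsor is that the reported rate may be slightly less favourable.
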